10.4.2 SEL-110.36 Preparation

Each vial of SEL-110.36 will be reconstituted with 4.9 mL of sterile water for injection, USP (United States Pharmacopeia or equivalent) which forms a 2 mg/mL suspension before being drawn into appropriate size syringe/syringes for IV infusion with syringe pump. Reconstituted SEL-110.36 is stable for 24 hours at room temperature at normal light conditions. SEL-110.36 should be administered on the same day and as soon as possible after reconstitution. If not administered immediately, store refrigerated. The SEL-110.36 dose must be completely administered within 12 hours of the start of reconstitution.

10.4.3 KRYSTEXXA Preparation

Doses of KRYSTEXXA will be calculated and prepared based on the manufacturer's currently approved labeling (*KRYSTEXXA Prescribing Information 2018*).

Under appropriate aseptic technique, 1 mL of KRYSTEXXA will be withdrawn from the vial and injected into a single 250 mL bag of 0.9% Sodium Chloride Injection, USP or 0.45% Sodium Chloride Injection USP for IV infusion. The solution will not be mixed or diluted with other drugs. Thorough mixing will be by inversion, not shaking. The diluted solution may be kept for 4 hours at 2°C to 8°C (36°F to 46°F) and at room temperature (20°C to 25°C, 68°F to 77°F). It is recommended that diluted solutions be stored under refrigeration, not frozen, protected from light, and used within 4 hours of dilution.

Detailed procedures for study drug preparation are provided in the Study Operations Manual.

10.5 Premedication

10.5.1 Gout Flares (Prevention and Treatment)

All patients that meet all inclusion and exclusion criteria will be premedicated for gout flare prevention. The regimen will begin at least 7 days prior to the first dosing of study drug and continue for as long as the patient is participating in the clinical study.

Patients not already taking colchicine will receive colchicine 1.2 mg as a single loading dose followed by 0.6 mg QD for the remainder of participation in the trial. If the patient cannot tolerate the loading dose level of 1.2 mg, then the patient will initiate and maintain colchicine at 0.6 mg. Patients with a documented medical reason that describes a contraindication to colchicine will receive ibuprofen 600 mg TID or an equivalent NSAID unless the patient has a contraindication to NSAID. At the discretion of the Investigator, a proton pump inhibitor may be prescribed with the NSAID as gastric prophylaxis. Patients with documented medical reasons that describe contraindications to both colchicine and NSAIDs will receive no premedication for gout flare.

Patients who began receiving a NSAID as gout flare prevention medication due to a contraindication to colchicine should continue to receive the NSAID during study participation. These medications will be supplied by the clinic.

As gout flares are expected to occur despite preventative premedication, incidents of gout flare are to be recorded as an AE and treated at the discretion of the Investigator to provide adequate patient care.

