5.4 Impact on Quality of Life

One longitudinal study in this patient population reports that approximately 70% of patients with chronic refractory gout have at least 1 tophus and an average of 7 flares per year. In a separate study of chronic refractory gout, patients self-reported more than 60% of these flares as crippling ([Brook 2010](#)). Symptoms of pain, limited mobility, and disability are debilitating and deeply affect physical function and emotional and social functioning, and disease severity correlates with a marked compromise in quality of life ([Strand 2012](#), [Becker 2009](#)).

The relationship between self-reported quality of life and disability and disease severity have been evaluated in multiple clinical studies. Over 100 subjects with chronic refractory gout evaluated using the Medical Outcomes Study Short Form-36 assessment, and results revealed that patients with chronic refractory gout have significantly lower subscales analogous to those of 75-year old individuals ([Becker 2009](#)). Specifically, disease severity, as characterized by number of flares in the past year, number of tender or swollen joints, or presence of tophi, significantly correlates with worse quality of life scores in all areas, which include bodily pain, general health, mental health, physical functioning and vitality. Subjects with comorbidities

experienced worse physical functioning. Notably, their scores did not improve over the 52-week period despite undergoing maximal medical management (*Strand 2012*).

There is also evidence that gout affects workplace productivity, as studies in patients with chronic, refractory gout self-report work absences due to flares, losing 25.1 workdays on average per year. Another study specifically found employees with gout missed 4.56 more days of work per year than those without gout (*Edwards 2011*).

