11.2 Gout Assessment

11.2.1 Gout Flare Assessment

Gout flare will be assessed as part of TEAE collection with severity determined as described in [Section 12.2.2.3](#).

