12.2.1.5 Infusion Reactions / Adverse Events of Special Interest

A study drug-related AE that occurs within 24 hours after initiation of study drug infusion will be assessed as an infusion reaction. An infusion reaction suspected to be anaphylaxis will be assessed according to the clinical criteria for the diagnosis of anaphylaxis based on the National Institute of Allergy and Infectious Diseases (NIAID) / Food Allergy & Anaphylaxis Network (FAAN) Symposium criteria ([Sampson 2006](#)).

Infusion reactions will be managed and treated as described below. In addition to premedication with antihistamines and steroids ([Section 10.5.2](#)), the following steps will be implemented in this protocol to either reduce the risk of infusion reactions or manage infusion reactions.

- Patients with immunoreactivity to PEG will be ineligible for the study
- Patients with prior exposure to uricase therapy will be ineligible
- Patients with a history of anaphylaxis or severe allergic reactions, angioedema, or previous infusion reactions will be excluded from the trial.
- Study drug will be administered at controlled rates only in a healthcare setting and by healthcare providers sufficiently equipped and prepared to manage infusion reactions including anaphylaxis.
- In case of infusion reaction, sites will perform specific assessments as specified in the Study Operations Manual.
- Each patient will be observed for infusion reactions after dosing of study drug in the clinic for approximately 1 hour after the end of study drug infusion. Patients will be informed about the signs or symptoms of infusion reactions and will be instructed to notify the Investigator immediately if they believe they are experiencing a reaction.
- Each patient shall remain for a minimum of 1 hour after the completion of infusion of study drug for a period of safety observation.
- Only sites with immediate capability to appropriately respond to a reaction of this severity will be allowed to participate in the trial to reduce the risk to any patient.

Adverse events of special interest (AESI) will be recorded specifically for occurrences of: gout flares, infections, viral infections, interstitial lung disease, stomatitis, infusion-related reactions including anaphylaxis, malignancies, renal failure; and the following lab tests, if deemed

clinically significant by the PI: hyperlipidemia, worsening of renal function tests, proteinuria, and leukopenia.

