13.4.2 Secondary Efficacy Endpoints and Analyses

The secondary endpoints of this study are:

- Comparison in the percentage of patients on SEL-212 vs. KRYSTEXXA who achieve and maintain reduction of SUA < 6 mg/dL for at least 80% of the time during Treatment Period 6
- Comparison in the percentage of patients on SEL-212 vs. KRYSTEXXA who achieve and maintain reduction of SUA < 6 mg/dL for 100% of the time during Treatment Period 6
- Comparison in the percentage of patients on SEL-212 vs. KRYSTEXXA who achieve and maintain reduction of SUA < 6 mg/dL for at least 80% of the time during Treatment Period 3
- Comparison in the percentage of patients on SEL-212 vs. KRYSTEXXA who achieve and maintain reduction of SUA < 6 mg/dL for 100% of the time during Treatment Period 3
- Comparison between patients on SEL-212 vs. KRYSTEXXA in pre-dose SUA values > 6 mg/dL during Treatment Periods 2-6. The pre-dose SUA is collected on the dosing day prior to the dosing administration or it is collected at the visit where dosing would have occurred had the patient not been previously withdrawn from study drug.
- Comparison between patients on SEL-212 vs. KRYSTEXXA of the change in health questionnaires
- Comparison between patients on SEL-212 vs. KRYSTEXXA of gout flare incidence per 3-month period (Treatment Periods 1-3 and Treatment Periods 4-6)
- Comparison between patients on SEL-212 vs. KRYSTEXXA of gout flare frequency per 3-month period (Treatment Periods 1-3 and Treatment Periods 4-6)
- Comparison between patients on SEL-212 vs. KRYSTEXXA of the change from Baseline to Treatment Period 6 in number of tender joints
- Comparison between patients on SEL-212 vs. KRYSTEXXA of the change from Baseline to Treatment Period 6 in number of swollen joints

All statistical tests in secondary endpoints for the comparison between SEL-212 and KRYSTEXXA will be performed using one-sided tests at a type 1 error rate level of $\alpha=5\%$. In addition, 90% confidence intervals for treatment differences between SEL-212 and

KRYSTEXXA treatment groups will be computed. The efficacy analyses will be carried out based on the ITT and PP Sets. mITT analyses will be performed if appropriate.

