8.3. Adverse Events / Adverse Drug Reactions

All AEs will be coded and grouped into Preferred Terms (PT) by System Organ Class (SOC), using the most recent MedDRA Version. All AEs will be summarized by treatment, SOC and PT. A treatment-emergent AE (TEAE) is an AE that starts or worsens at any time after initiation of study drug on Day 0 of Treatment Period 1 until the End of Study Visit (30 days after completion of the last dose of study drug).

An overall summary will be provided of the number and percentage of patients reporting TEAEs, serious TEAEs, treatment-related (possibly related and related) TEAEs, Adverse events of special interest (AESIs), TEAEs leading to study drug withdrawal, and TEAEs leading to death. AESIs will be defined by medical monitor prior to database lock.

The number and percentage of patients with TEAEs / serious TEAEs / TEAEs leading to study drug withdrawal/treatment-related TEAEs will be summarized by SOC and PT for each treatment group (SEL-212 or KRYSTEXXA®). AESIs will also be summarized.

TEAEs will also be summarized by maximum intensity and causality.

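### Gout flares, an efficacy endpoint, sit inside the any-TEAE, AESI and maximum-intensity summaries, and no flare-excluded version is planned

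*Protocol*

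**What the plan says.** Flares enter the safety data by design. Protocol 10.5.1 states: "As gout flares are expected to occur despite preventative premedication, incidents of gout flare are to be recorded as an AE". Protocol 11.2.1 adds that "Gout flare will be assessed as part of TEAE collection", with severity graded on the general AE scale of 12.2.2.3. Protocol 12.2.1.5 puts flares first on its AESI list: "Adverse events of special interest (AESI) will be recorded specifically for occurrences of: gout flares, infections, viral infections".

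Flares are also efficacy data. Protocol 13.4.2 lists flare incidence and flare frequency per 3-month period as secondary endpoints, and SAP 7.2.5 analyses both, including by severity.

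The safety endpoint in Protocol 6.2.3 and SAP 4.3 is comparative: tolerability of SEL-212 against Krystexxa, judged by AEs, SAEs, deaths and discontinuations due to AEs. For reporting, SAP 8.3 plans: "An overall summary will be provided of the number and percentage of patients reporting TEAEs, serious TEAEs, treatment-related (possibly related and related) TEAEs", followed by AESIs, TEAEs leading to study drug withdrawal and TEAEs leading to death. It adds SOC and preferred-term tables, and says "TEAEs will also be summarized by maximum intensity and causality". On the AESI definition it says "AESIs will be defined by medical monitor prior to database lock". Neither document removes flares from any of these counts or plans a version without them.

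Three further statements bear on the point. Protocol 7.7 lists a substantially lower flare rate among the improvements of SEL-212 over available therapy. Protocol 7.6.3.2 describes flares in the Phase 2 study as low in incidence, without a figure. Protocol 5.5 names flares next to infusion reactions when it describes the common adverse reactions of Krystexxa.

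**The concern.** A total that counts a patient once for any event cannot distinguish a flare from an infection, a stomatitis or an infusion reaction. If flares are common in both arms, most of the room for a difference in other harms is used up. If flares differ by arm, as the protocol's benefit section suggests they will, the total moves for a reason already reported under efficacy. The two effects can also cancel.

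At stake is the reading of the comparative tolerability endpoint. A reader of the clinical study report would normally look at the any-TEAE, AESI and worst-grade rows first. Under the current plan, none of these answers how many patients on each arm had a harm other than a flare, or how severe the worst such harm was.

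**Working it through.** **Plan's own figure.** The documents give no expected incidence for TEAEs or for on-study flares, so there is no planning figure to reproduce on this point. The stated sample size (65% versus 44%, one-sided 5%, 80% power, 69 per group) does reproduce at 69, but nothing here depends on it. The 75 per arm to be randomized is used below only as a gauge.

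**Step 1: which summaries contain flares.**

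| Summary in SAP 8.3 | Does a flare count? |
|---|---|
| Any TEAE | Yes, if in the TEAE window |
| AESI | Yes, if the medical monitor keeps the list in Protocol 12.2.1.5 |
| Maximum intensity | Yes, whenever the flare is the patient's worst-graded event |
| Treatment-related, causality | Counts as related only when judged possibly related or related |
| Serious, leading to withdrawal, leading to death | Only when the flare meets that criterion |

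**Step 2: how common flares might be.** The only rate in the documents is a disease-background figure in Protocol 5.4: "approximately 70% of patients with chronic refractory gout have at least 1 tophus and an average of 7 flares per year". The lower rates of 3.5 and 1.75 per year are assumptions (one half and one quarter of 7), to allow for prophylaxis and treatment. With m = rate × 168/365.25, the chance of at least one flare is 1 − exp(−m) under a Poisson model, and 1 − (1 + k·m)^(−1/k) under a negative binomial with dispersion k.

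| Rate per year | m | Poisson | k = 0.5 | k = 1 | k = 2 |
|---|---|---|---|---|---|
| 7 | 3.22 | 96% | 85% | 76% | 63% |
| 3.5 (assumed) | 1.61 | 80% | 69% | 62% | 51% |
| 1.75 (assumed) | 0.80 | 55% | 49% | 45% | 38% |

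The range is about 40% to 96%. It is lower for a patient who stops early, because the TEAE window closes 30 days after the last dose. With a 58-day window (last dose on Day 28), the Poisson figures are 67%, 43% and 24%.

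**Step 3: masking, with equal flare incidence f in both arms.** Let q be the proportion with a non-flare TEAE. Under independence, P(any TEAE) = 1 − (1 − f)(1 − q), so the difference shown is (1 − f) times the difference in q. Take q = 60% versus 40% (assumed).

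| f | Any TEAE | Difference shown |
|---|---|---|
| Flares excluded | 60% v 40% | 20 points |
| 20% | 68% v 52% | 16 |
| 40% | 76% v 64% | 12 |
| 60% | 84% v 76% | 8 |
| 80% | 92% v 88% | 4 |
| 96% | 98.4% v 97.6% | 0.8 |

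As a gauge of visibility only, since no test is planned for these tables: with 75 per arm and two-sided 5%, power for the contrast is 69% with flares excluded, 36% at f = 40% and 13% at f = 80%.

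Independence matters. If flares and other TEAEs overlapped as far as possible, P(any TEAE) would be the larger of f and q. At f = 40% that gives 60% versus 40%, so nothing is lost. At f = 80% it gives 80% versus 80%, so everything is lost.

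**Step 4: a difference created by flares alone.** With q = 50% in both arms and f = 40% versus 60%: 1 − 0.6 × 0.5 = 70% against 1 − 0.4 × 0.5 = 80%.

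**Step 5: cancellation.** With q = 60% on SEL-212 and 40% on Krystexxa, and f = 40% and 60% respectively: 1 − 0.6 × 0.4 = 76% against 1 − 0.4 × 0.6 = 76%. A 20-point excess of other harms leaves no trace, at moderate flare rates.

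**Step 6: can the planned tables recover the missing figure?** A patient can appear in several preferred-term rows. The row counts therefore only bound the number of patients with any non-flare TEAE: at least the largest single row, at most the sum of the rows. A patient's worst non-flare grade cannot be read from term rows either. Both need patient-level data, and no planned summary gives them.

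**The case against.** The strongest reply is that other harms are not hidden. SAP 8.3 tabulates TEAEs, serious, related and withdrawal events by SOC and preferred term. Infections, stomatitis and infusion reactions are protocol AESIs. SAP 6.1 adds Kaplan-Meier figures with log-rank tests for termination due to AEs and for discontinuation due to stopping rules or infusion-related reactions. The TEAE summaries carry no test, and no section makes any-TEAE the decisive safety measure. All of this stands, and it limits the severity. It does not supply the patient-level count of step 6.

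A second reply is that a flare is a genuine harm. Protocol 5.5 lists it with Krystexxa's common adverse reactions, so a flare difference is part of tolerability. This also stands. Recording flares as AEs is not an error, and a tolerability statement based only on flare-excluded tables would drop a recognised reaction.

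A reader might infer several stronger things that the documents do not support:
- **That every overall TEAE total is affected.** Serious, withdrawal and death rows, and the related row, take in a flare only if it qualifies. For causality, Protocol 12.2.2.2 tells the investigator to weigh the natural history of the disease.
- **That most patients will flare, so the totals are nearly saturated.** Protocol 10.5.1 expects flares to occur but gives no incidence. The rate of 7 per year is background, and Protocol 7.6.3.2 and 7.7 point to low or reduced flares on SEL-212.
- **That flares will dominate the maximum-intensity table because patients elsewhere called most of them crippling (Protocol 5.4).** That is self-report from a separate study. Grading here follows the Rheumatology Common Toxicity Criteria.

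**Conclusion.** The point holds as a gap in reporting, of minor severity. Flares are counted in the any-TEAE and maximum-intensity summaries, in the AESI summary if the protocol's list is kept, and among treatment-related events when judged related. No flare-excluded counterpart is planned, although the safety endpoint is comparative and the protocol itself suggests that flares will differ by arm.

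The possible distortion ranges from small to large. A 20-point difference in other harms shows as 16 points at 20% flare incidence and as 0.8 points at 96%, and a 10-point difference can arise from flares alone. These sizes rest on assumed non-flare rates, assumed flare rates and independence. They show what can happen, not what is likely. No confirmatory conclusion is affected.

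**What to change.** In SAP 8.3, add a second version of five summaries, each excluding gout-flare preferred terms: overall, treatment-related, AESI, maximum intensity and causality. Fix the list of excluded terms before database lock. Because the SAP leaves the AESI definition to the medical monitor while the protocol gives a list, state at the same time whether flares belong to it.

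Keep the existing all-TEAE tables and report both versions when describing comparative tolerability. The flare-excluded tables should not replace the totals, since flares are also a recognised adverse reaction. Flares continue to be reported under SAP 7.2.5.

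The cost is a few extra tables from one filter on existing programs, with no new data and no change to conduct.

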10.5.2 Premedication with Antihistamines and Steroids

All patients in the study will be pre-medicated with oral antihistamines and steroids as follows for prevention of infusion reactions:

- Prednisone (40 mg) orally approximately 24 (\pm 12) hours prior to dosing (morning before study drug dosing on Day 0)
- Fexofenadine (180 mg) orally approximately 12 (\pm 2) hours prior to dosing (evening before study drug dosing on Day 0)
- Fexofenadine (180 mg) orally approximately 2 (\pm 1) hours prior to dosing (day of study drug dosing)
- Methylprednisolone (40 mg) (or equivalent) IV approximately 1 (\pm 0.5) hours prior to dosing (day of study drug dosing)

Refer to [Section 12.2.1.5](#) for guidance on reducing the risk of infusion reactions and for managing infusion reactions.

10.6 Administration

10.6.1 SEL-212

Before administration of SEL-212, patients will be premedicated with antihistamines and steroids as described in [Section 10.5](#).

Patients will receive treatment with SEL-212 on Day 0 of each Treatment Period for a total of 6 doses of study drug.

All study drugs should be administered through the same IV access. All blood samples should be drawn from an alternative venous access.

If an infusion reaction occurs, Investigators are permitted to use concomitant medications or treatments deemed necessary to provide adequate patient care. Investigators should also utilize the infusion reaction lab kit provided in the Study Operations Manual to collect additional blood specimens. In the case of a Grade 3 or 4 infusion reactions occurring during an infusion, the administration of study drug should be immediately discontinued, and the affected patient should be treated according to the clinical trial site's protocol for infusion reactions (e.g., monitoring, administration of antihistamines, corticosteroids, fluids and epinephrine, as clinically indicated).

The reconstituted SEL-110.36 will be withdrawn from the vial and dosed via IV infusion with a syringe infusion pump utilizing an appropriately sized syringe. SEL-110.36 will be infused at a rate of 3.0 mL/hr for the first 30 minutes, then a rate adequate to deliver the remaining dose volume over a period of 60 minutes concurrently with 125 mL normal saline. Following the infusion of SEL-110.36, the main IV line must be flushed with normal saline prior to the start of the SEL-037 infusion. Refer to the Study Operations Manual for instructions regarding infusions for patients with medical history involving cardiovascular comorbidities.

SEL-037 infusion will start within 15 minutes after completion of the SEL-110.36 infusion. SEL-037 will be infused via infusion pump over a time period of no less than 120 minutes. If an infusion reaction occurs during the administration of SEL-037, the infusion may be slowed, or stopped and restarted at a slower rate at the discretion of the physician. Following the infusion of SEL-037, the main IV line must be flushed with normal saline.

The Investigator is permitted to modify the infusion parameters (decrease the rate of infusion or interrupt the infusion) **ONLY** if medically warranted in response to an AE. The Investigator will notify the unblinded medical monitor of any changes in infusion parameters. Detailed instructions for modifying the infusion parameters are included in the Study Operations Manual.

